Promoting Altruism to Enhance Vaccine Acceptance NCT04568590 Study Protocol and Statistical Analysis Plan Document Date: 6/27/22

Cohort Study to Determine the Effect of an Educational Intervention Focusing on Herd Immunity to Enhance Vaccination Uptake Rates

Principal Investigator(s), Resident Investigator:

[name], MS, Co-Principal Investigator [name], Co-Principal Investigator [name], DO, Resident Investigator

Sponsor or Funding Source: Center for Vaccines at the Extremes of Aging Pilot Funds

Background, Rationale, and Context

Vaccine hesitancy is on the rise in the United States, which is causing a resurgence of vaccine-preventable diseases. Vaccine hesitancy regarding the seasonal influenza vaccine is especially prevalent, with a recent study indicating hesitancy prevalence of 6.1% for routine childhood vaccines but 25.8% for influenza vaccine¹⁻⁶. This trend is particularly concerning today as the world awaits a COVID-19 vaccine, the effectiveness of which will be critically threatened by poor uptake due to vaccine hesitancy. Uniform strategies to address vaccine hesitancy have met challenges due to pervasive online misinformation, and the heterogeneity of the vaccine-hesitant community, which crosses racial, socioeconomic, educational, and political lines^{3, 7-26}. However, a common thread that globally may contribute to vaccine hesitancy is rising individualism, the moral stance that the individual takes precedence over a larger social group²⁷⁻²⁹. Altruistic, prosocial motivation seems to be an essential component of vaccine acceptance³⁰. Altruism has also been identified as the major motivator in subjects willing to participate in preventative vaccine trials³¹. One potential strategy to increase altruism amongst vaccine hesitant individuals is to provide education on the concept of herd immunity. A recent scenario study found that explicitly communicating the role of herd immunity increased people's intention to accept vaccines, especially in Western, individualist cultures³². Strategies like this to promote altruism in order to enhance vaccine uptake could improve public health outcomes. How to best communicate the benefits of herd immunity in an increasingly individualistic, nationalistic climate is unclear but must be addressed.

Pediatric oncology patients represent a potentially excellent population on whom to base a herd immunity educational effort aimed at enhancing altruism in vaccine-hesitant parents: pediatric cancer patients tend to elicit strong sympathetic responses from the public; they come from all communities in the US and are therefore local; and they rely on herd immunity for protection from vaccine-preventable infections because they are largely unable to receive vaccines due to their immunocompromised state³³⁻⁴⁶. Therefore, we hypothesize that a brief educational encounter on herd immunity focusing on local pediatric cancer patients' risk and sponsored by local pediatric oncology providers will increase altruism scores and directly correlate with an increase in seasonal influenza vaccine acceptance. We aim to explore the overall effectiveness of this educational intervention, and also aim to explore whether there may be an identifiable subpopulation most amenable to this type of intervention based on baseline altruism score, race, educational level, or political affiliation.

Objectives

Specific Aim 1: To identify associations with influenza vaccine hesitancy, including parental demographics and altruism score, in families with healthy children attending two pediatric practices.

Specific Aim 2: In the cohort of families with baseline vaccine hesitancy, to assess the effectiveness of a pilot educational intervention focusing on the development of herd immunity for pediatric oncology patients by measuring:

- a. The change in vaccine hesitancy scores pre- and post-intervention.
- b. The change in the score of question number 6 on the Vaccine Hesitancy Scale, which uniquely and specifically relates to altruism. We will also compare the change in this individual score

with the change in the other individual question scores, which relate to other realms of vaccine confidence, including safety, efficacy, and trust.

c. The rate of influenza vaccine uptake compared to historic controls from previous influenza seasons.

Exploratory Aim: In an effort to further understand the complex interaction between study volunteers (interviewing medical students) and study subjects, including how unique interactions between the study representative(s) and the study subjects may affect questionnaire responses and vaccine acceptance decisions, we aim to conduct motivational interviews with 20 vaccine-hesitant participants, and with four study volunteers. Each motivational interview will be conducted by [name], PhD, Associate Professor and Chair of the Department of Communication at Wake Forest University.

We aim to explore the relationship between baseline influenza vaccine hesitancy rates and baseline altruism scores. Effectiveness of our intervention is dependent on parental altruism levels; therefore, we also seek to determine if there is an association between parental altruism and vaccine hesitancy for their children.

Methods and Measures

Setting:

Study subjects will be recruited from two Wake Forest University Baptist Medical Center general pediatric practices: Westgate Pediatrics and Pediatrics - Ford, Simpson, Lively, and Rice. Westgate Pediatrics is located at [name]. Westgate serves a diverse population, with approximately 50% of patients receiving Medicaid services. Pediatrics - Ford, Simpson, Lively, and Rice is located at [name]. This latter practice serves a large population that is generally of a higher socioeconomic status than Westgate Pediatrics, with approximately 25% of patients receiving Medicaid services. Study volunteers will be Wake Forest School of Medicine medical students in their 4th year who volunteer to participate in this project as credit for a 4th year elective rotation.

Design:

A single-arm prospective cohort study will be conducted. The study will enroll as study subjects legal guardians of children who are influenza vaccine-eligible to measure their vaccine hesitancy scores, altruism scores, and the impact of an educational intervention focused on herd immunity on the guardians' vaccine hesitancy score.

Inclusion Criteria:

All legal guardians of children aged 6 months and up who are influenza vaccine-eligible and present to the pediatric clinic.

Exclusion Criteria:

Legal guardians of children who are not influenza vaccine-eligible including children less than 6 months of age, children on immunosuppressive medications, and children with underlying medical conditions resulting in an immunocompromised state.

Sample Size:

Specific Aim 1: baseline vaccine hesitancy is 25%⁴⁷. Clinically meaningful difference in hesitancy is defined as 15%. This difference can be detected with 80% power with 250 subjects per group.

Specific Aim 2: We anticipate our intervention could reduce vaccine hesitancy from the national baseline of 25% to 15% on the post-intervention survey. Identifying this reduction from 15% to 15% in paired proportions with 80% power requires enrollment of 312 subjects who complete both tests (i.e. enrolling 312 subjects identified as vaccine-hesitant).

Exploratory Aim: Motivational interviews with study subjects (20) and study volunteers (4) will not be powered or statistically analyzed.

Interventions and Interactions

We will conduct a prospective cohort study of families with children aged 6 months and up who are eligible to receive the seasonal influenza vaccine. Subjects who consent to this study will answer questions which will include demographic questions, a baseline 20-item Altruism Scale, and an 8-item Vaccine Hesitancy Scale. The 20-item Altruism Scale will be scored based on a 5-point Likert scale, with each question scoring from 1-5, then added together to give a cumulative score. Higher scores indicate higher altruism. The Vaccine Hesitancy Scale will be scored as previously described: scoring responses for each item will be scored as follows: strongly agree = 1, agree = 2, disagree = 4, and strongly disagree = 5, such that higher values always indicated greater hesitancy. We will then calculate the average score of the 8 items included in the scale, and use the pre-defined average score of ≥ 3 as "hesitant." Subjects identified as vaccine-hesitant based on a Vaccine Hesitancy Score ≥ 3 will be given an educational handout and provided a standardized, brief educational session overviewing the educational handout. At the end of the doctor's visit, subjects will complete a second identical 8-item Vaccine Hesitancy Scale.

We will also conduct a retrospective chart review of all patients who participated in the initial survey to determine whether the child received the influenza vaccine. Retrospective chart review will also be conducted to estimate the influenza vaccine acceptance rates for each pediatrics practice over the same time period from one year prior.

Two study volunteers will be at each pediatric clinic. A volunteer will approach an eligible parent/guardian in the waiting room prior to their scheduled appointment and obtain informed consent to participate in the study. A consenting subject will complete the Vaccine Hesitancy Scale⁴⁷ orally with the study volunteer. The Vaccine Hesitancy Scale is positive if the average of all questions is greater than or equal to 3. When the study volunteer is inputting and grading the Vaccine Hesitancy Scale in a REDCap survey tool on an iPad, the subject will complete the Self-Report Altruism Scale⁴⁸ and several demographic questions on paper. If the guardian screens positive for vaccine hesitancy (i.e., vaccine hesitancy score average \geq 3), they will be given the informational handout along with a brief script. The parent will have the opportunity to review the intervention in the waiting room and during the visit while the provider is out of the room. If the guardian was deemed vaccine hesitant and was given the intervention, the study volunteer will remain at the nurse's station and wait for the visit to be completed. Once the family is finished, the study volunteer will approach the participant once again and complete the Vaccine Hesitancy Scale orally prior to check out. The subject's child's electronic health record will then be accessed to document whether that patient received the seasonal influenza vaccine that day.

Following study volunteer participation and subject participation in the study, up to four study volunteers and up to 20 vaccine-hesitant study subjects will be contacted by [name], PhD, to request an interview. The interviews will take place virtually, by phone or video, by [name]. Study subjects will have already provided written consent to this interview, but [name] will review the purpose of this phone call and provide an opportunity for study subjects to opt out. All study volunteers will be provided a Study Information Sheet when they orient as study volunteers on this project, which details the purpose of the research project and that up to four of the volunteers, [name] will review/re-provide a Study Information Sheet, detailing the purpose of the interview, but there will be no written consent for the study volunteers.

Analytical Plan

For Specific Aim 1, our primary outcome is vaccine hesitancy, which is dichotomized as hesitant (mean score \geq 3) or not hesitant (mean score \leq 3) based on results of the Vaccine Hesitancy Scale. Exposures will

include general demographic and clinical characteristics along with the Self-Report Altruism Scale (expresses as a continuous score from 20 to 100). The children's clinical status will be categorized using the Pediatric Medical Complexity Algorithm v3.1⁴⁹. Results will be analyzed initially using descriptive statistics to determine the prevalence of hesitancy. Associations between hesitancy and potential exposures will be assessed using chi square or ANOVA. Associations found to be statically significant in the bivariate analysis will be incorporated into a mixed-effects multivariable logistic regression model, which will treat practice location as a random effect. A p value of 0.1 will be used for inclusion of variables in the model; otherwise, a p value <0.05 will be the cutoff for statistical significance.

For Specific Aim 2, our primary outcome will be the change in vaccine hesitancy scores pre- and postintervention, which will be assessed with a paired t-test or Wilcoxon signed-rank test, following review of the score distribution. We will also measure the change in Question #6 (the only Altruism-specific question on the questionnaire) independently, and also compared with each other individual question on the questionnaire, and pre- and post-intervention change will be assessed with a paired t-test or Wilcoxin signranked test, following review of the score distribution. As a secondary outcome, the rate of influenza vaccine uptake will be compared qualitatively to historic controls.

For the Exploratory Aim, we will capture qualitative data and seek trends. No statistical computation will be done on these data.

All data will be entered directly into a Research Electronic Data Capture database and analyzed using SAS v9.4 (Cary, NC).

Human Subjects Protection

Risks for participation are not more than minimal. There is risk of accidental unauthorized release of identifiable personal information. Data access will be limited to study staff. Data and records will be kept locked and secured, with any computer data password protected. Participation in a post-study interview by the study volunteers will not require written consent, but it is voluntary. The grading for the elective course is Pass/Fail, and will be exclusively based on their participation in the actual study, and not the post-study interview, which is voluntary.

Subject Recruitment Methods

All parents who present to either pediatric clinic with children 6 months and up who are eligible for the flu vaccine will be eligible to participate in the study. Two student volunteers will be at each clinic for the recruitment process during flu season (between October and December depending on volunteer schedule availability). A volunteer will approach any parent(s) in the waiting room prior to their schedule appointments to recruit for the study regardless of gender or race/ethnicity.

For the retrospective chart review, there is minimal risk involved to participants. All protected health information will be de-identified prior to data analysis and publications; subject identity will be known only to the study staff. Subjects who participated in the initial arm of the study will be included in the chart review to determine further demographic data and whether the child received the flu vaccine.

Informed Consent

Signed informed consent will be obtained from the parent/guardian for the parent's participation in the study and for permission to access EMR data for their child. A study volunteer not actively involved in the child's medical care will obtain the informed consent. The informed consent will be obtained in person in the waiting room of the outpatient pediatric clinic prior to the scheduled clinic visit.

A Study Information Sheet will be provided to the study volunteers when they orient to their roles on this project, including that they may be asked to be interviewed by [name] following their participation. They will be told this is voluntary, and will have no bearing on their grade. Immediately prior to their interview, [name] will again review the study information sheet with the study volunteer, and ask for permission to proceed with the interview. No written consent will be obtained from the study volunteer.

Confidentiality and Privacy

Confidentiality will be protected by collecting only information needed to assess study outcomes, minimizing to the fullest extent possible the collection of any information that could directly identify subjects, and maintaining all study information in a secure manner. To help ensure subject privacy and confidentiality, only a unique study identifier will appear on the data collection form. Any collected patient identifying information corresponding to the unique study identifier will be maintained on a linkage file, store separately from the data. The linkage file will be kept secure. with access limited to designated study personnel. All of the individual participant data collected during the trial, after deidentification, will be available. The Study Protocol, Statistical Analysis Plan, and Informed Consent Form will also be available. All data will be available beginning 9 months and ending 36 months following article publication. The study team intends to share with researchers who provide a methodologically sound proposal to achieve aims in the approved proposal. Proposals may be submitted up to 36 months following article publication. Subject identifying information will be destroyed three years after study publication by removing the dataset from REDCap, consistent with data validation and study design, producing an anonymous analytical data set. Direct data access will be limited to study staff. Data and records will be kept locked and secured, with any computer data password protected. No reference to any individual participant will appear in reports, presentations, or publications that may arise from the study.

Data and Safety Monitoring

The principal investigator will be responsible for the overall monitoring of the data and safety of study participants. The principal investigator will be assisted by other members of the study staff.

Reporting of Unanticipated Problems, Adverse Events or Deviations

Any unanticipated problems, serious and unexpected adverse events, deviations, or protocol changes will be promptly reported by the principal investigator or designated member of the research team to the IRB and sponsor or appropriate government agency if appropriate.

References

1. Callender D. Vaccine hesitancy: More than a movement. *Hum Vaccin Immunother*. Sep 2016;12(9):2464-8. doi:10.1080/21645515.2016.1178434

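### Aim 1's sample-size figures do not agree: 250 per group at 80% power fits 25% versus 15% (10 points), not the stated 15% difference from 25%

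*Combined protocol and SAP*

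**What the plan says.** The Sample Size section, Specific Aim 1, sets baseline hesitancy at 25% and continues: "Clinically meaningful difference in hesitancy is defined as 15%. This difference can be detected with 80% power with 250 subjects per group". It gives no comparison rate, direction, significance level, sidedness or definition of the groups.

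The Specific Aim 2 paragraph directly below uses 15% as a rate and not as a difference: "We anticipate our intervention could reduce vaccine hesitancy from the national baseline of 25% to 15% on the post-intervention survey". It asks for 312 completers, glossed as "enrolling 312 subjects identified as vaccine-hesitant".

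The Analytical Plan for Aim 1 dichotomizes hesitancy and says: "Associations between hesitancy and potential exposures will be assessed using chi square or ANOVA". After a variable-selection threshold of 0.1, it adds: "otherwise, a p value <0.05 will be the cutoff for statistical significance". The Design section describes a single-arm cohort.

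**The concern.** A baseline rate, a difference, a power and a test level together fix the size per group. Here the size stated is far larger than a 15-point difference needs, and it equals the size for a 10-point difference. A reader therefore cannot tell which effect Aim 1 was designed to detect.

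If 15 points is meant, the stated power is wrong. If 10 points is meant, the stated clinically meaningful difference is wrong. That difference is the only benchmark the plan gives for reading an Aim 1 association. An association of 10 to 14 points would fall short of the written benchmark even though the study may have been sized to find one of 10.

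The two groups are also unnamed. Aim 1 looks for associations within one cohort, across several demographic and clinical exposures and a continuous altruism score. No single pair of equal groups follows from that design.

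**Working it through.** **Inputs.** From the Sample Size section, Aim 1: baseline p1 = 0.25, difference 15%, power 80% (z = 0.8416), n = 250 per group. From the Analytical Plan: significance at 0.05 and a chi-square test. Assumed, because not stated: a two-sided test (z = 1.9600) and equal groups, as a single per-group figure implies.

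**Formula.** Two-proportion z-test with pooled null variance and no continuity correction, where p̄ = (p1 + p2)/2:

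n per group = [1.9600·√(2p̄(1−p̄)) + 0.8416·√(p1(1−p1) + p2(1−p2))]² / (p1 − p2)²

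**Reproducing the stated 250 (25% versus 15%).** p̄ = 0.20.
- First term: 1.9600 × √0.3200 = 1.1087
- Second term: 0.8416 × √0.3150 = 0.4724
- n = (1.5811)² / 0.10² = 2.4998 / 0.0100 = 249.98, so **250**

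**The difference as written, 15 points.**
- 25% versus 10% (p̄ = 0.175): (1.0532 + 0.4433)² / 0.15² = 2.2397 / 0.0225 = 99.5, so **100**
- 25% versus 40% (p̄ = 0.325): (1.2982 + 0.5503)² / 0.15² = 3.4171 / 0.0225 = 151.9, so **152**

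**Read as a relative 15%.** 25% versus 21.25%: (1.1687 + 0.5013)² / 0.0375² = 1,983.3, so **1,984**. Upward, 25% versus 28.75% needs 2,193.

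**Power at 250 per group.** Power = Φ[(|p1 − p2| − 1.9600·s0)/s1], with s0 = √(2p̄(1−p̄)/250) and s1 = √((p1(1−p1) + p2(1−p2))/250).

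| Contrast | s0 | s1 | Power | n per group for 80% |
|---|---|---|---|---|
| 25% vs 15% | 0.03578 | 0.03550 | 80.0% | 250 |
| 25% vs 10% | 0.03399 | 0.03332 | 99.4% | 100 |
| 25% vs 40% | 0.04189 | 0.04135 | 95.0% | 152 |
| 25% vs 21.25% | 0.03771 | 0.03767 | 16.7% | 1,984 |
| 25% vs 35% | 0.04099 | 0.04074 | 68.5% | 329 |

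Turned round, 250 per group at 80% power detects a fall of 10.0 points from 25% or a rise of about 11.5 points.

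**Does another standard method rescue 250 for 15 points?** No.
- Continuity correction gives 113 (25% vs 10%) or 165 (25% vs 40%).
- Unpooled variance gives 97 or 150, and the arcsine method 97 or 152.
- A one-sided 5% test gives 79 or 120.
- A different baseline does not help. At two-sided 5% and 80% power, a 15-point difference needs at most 174 per group, in the worst case of 42.5% versus 57.5%.
- Inflation for dropout or clustering would have to be 250/152 = 1.6 to 250/100 = 2.5 times, and none is stated.

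**Dependence on equal groups (illustration only).** Neither the total nor the split below is in the protocol. If 500 subjects in total were split 20:80, power would be 57–65% for 25% versus 15% and 81–95% for a 15-point difference; the ranges depend on direction and on which group has the 25% rate. If Aim 2's 312 hesitant subjects are all found, about 312/0.25 = 1,248 would be screened. At 20:80, 25% versus 15% would then have 94–95% power.

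**The case against.** The strongest reply is that little turns on this in practice. If 25% versus 15% was meant, 250 is correct. If 15 points was meant, 250 is more than enough. On neither reading is Aim 1 short of subjects with equal groups, and Aim 2's recruitment may take the cohort well past 500. No test or success rule uses the 15%, since Aim 1 is judged on p-values. The exact match to 250 also depends on the uncorrected pooled formula: unpooled and arcsine versions give just under 248, and continuity correction gives 270.

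Most of this is fair, and it limits the point. This is not a finding that Aim 1 is underpowered, and the 15% does not enter any analysis. The 20:80 figures are an illustration and not a property of the plan. The match to 250 should be described as the usual formula's result, not as the only possible one.

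The contradiction remains. No standard equal-group calculation at 5% and 80% gives 250 for a 15% difference, and nothing elsewhere in the document resolves it. The 15% is still the only meaningful difference stated for reading Aim 1's results.

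Direction also matters. Aim 1 exposures could raise or lower hesitancy, and 250 per group gives 80% power for a 10-point fall but only 68.5% for a 10-point rise.

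**Conclusion.** The concern holds. The four Aim 1 figures (25% baseline, 15% difference, 80% power, 250 per group) are mutually inconsistent. The stated size is 2.5 times (25% vs 10%) or 1.6 times (25% vs 40%) what a 15-point difference needs, and power at 250 would be 99.4% or 95.0%. The size agrees with 25% versus 15%.

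This rests on a two-sided 5% test and equal groups. The conclusion is unchanged under one-sided testing, continuity correction, or the unpooled and arcsine formulas. That the target rate was written in place of the difference is an inference from the Aim 2 paragraph, and the document does not confirm it. The point should be corrected, but it does not threaten the conduct of the study.

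**What to change.** State both rates, the direction, the significance level and sidedness, and which exposure groups are compared. Say that the figure assumes two equal groups.

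- **If 25% versus 15% was intended**, suggested wording is: *Baseline hesitancy is 25%. A clinically meaningful difference is 25% versus 15% (10 percentage points lower), detectable with 80% power (two-sided 5%) with 250 subjects in each of two equal groups.* Add that a 10-point increase (25% versus 35%) would need 329 per group, so that the statement is not read as covering both directions.
- **If 15 points was intended**, keep the difference and give its direction. Then restate either the size (100 per group for 25% versus 10%, 152 for 25% versus 40%, at 80% power) or the power at 250 per group (99% or 95%).

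The cost is wording in the first case and a restated size or power figure in the second. Data collection does not change.

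### The 80% power stated for Specific Aim 2 is for a 25%-to-15% fall in paired proportions, which matches neither the all-hesitant cohort nor the planned test of score change

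*Combined protocol and SAP*

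**What the plan says.** Four parts of the combined protocol and SAP bear on this point.

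- **Sample Size, Specific Aim 2.** The target is: "We anticipate our intervention could reduce vaccine hesitancy from the national baseline of 25% to 15% on the post-intervention survey". The next sentence says that identifying the reduction "in paired proportions with 80% power requires enrollment of 312 subjects who complete both tests (i.e. enrolling 312 subjects identified as vaccine-hesitant". That sentence prints the reduction as 15% to 15%. I take this as a slip for 25% to 15%, and nothing below depends on it.
- **Objectives, Specific Aim 2.** The aim is restricted by baseline status: "In the cohort of families with baseline vaccine hesitancy, to assess the effectiveness of a pilot educational intervention".
- **Interventions and Interactions.** The handout and session go only to guardians with a mean score of 3 or more. The second survey is described for the same people: "If the guardian was deemed vaccine hesitant and was given the intervention, the study volunteer will remain" at the nurse's station, and after the visit "the study volunteer will approach the participant once again and complete the Vaccine Hesitancy Scale orally prior to check out".
- **Analytical Plan, Specific Aim 2.** The "primary outcome will be the change in vaccine hesitancy scores pre- and postintervention, which will be assessed with a paired t-test or Wilcoxon signed-rank" test. Question 6 and the other items get the same kind of test. The only proportion in this part of the plan is uptake, and "the rate of influenza vaccine uptake will be compared qualitatively to historic controls".

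**The concern.** A power statement should describe the subjects who will be analysed and the test that will be applied to them. This one appears to do neither. The 25% is a population prevalence, while the analysed pairs are only those who screened positive. The calculation is for paired proportions, while the planned test is on score change.

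It is the only sample-size statement for the Aim 2 primary outcome. If it does not apply, the documents say nothing about the size of score change the study could detect. The target also loses a single meaning inside the hesitant cohort, because 25% to 15% can be translated into very different conversion rates.

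**Working it through.** **Inputs.** From Sample Size: 25%, 15%, 80% power and 312 completed pairs. The significance level is not given there. The Specific Aim 1 part of the Analytical Plan says "a p value <0.05 will be the cutoff for statistical significance", so I assume 5%, two-sided. The item scoring (1, 2, 4, 5; mean of 8 items) is from Interventions and Interactions. The documents give no SD, so SDs below are assumed.

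**1. Reproducing 312.** No formula is stated, so this step is inference. The McNemar normal approximation, with p10 and p01 the proportions switching in each direction, is

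n = [1.96·√(p10 + p01) + 0.8416·√(p10 + p01 − (p10 − p01)²)]² / (p10 − p01)²

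With p10 = 0.25 and p01 = 0.15:

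n = [1.96·√0.40 + 0.8416·√0.39]² / 0.01 = 311.6, so 312.

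This matches the plan's figure, but it has 25% moving from hesitant to non-hesitant and 15% moving the other way. If 0.25 and 0.15 are instead the before and after proportions, with independent responses, the switching proportions are 0.2125 and 0.1125 (total 0.325) and n = 253.

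**2. Applying it to the actual cohort.** Everyone starts hesitant, so the baseline proportion is 1 and p01 = 0 by design. The inputs in step 1 cannot occur. A paired-proportion test here is nearly empty: six switchers, all necessarily in one direction, give an exact two-sided p of 2·(1/2)⁶ = 0.031. At n = 312 that test has about 80% power when only 2.5% convert.

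**3. What 25% to 15% would mean in this cohort.**

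- If it describes all guardians surveyed and non-hesitant guardians stay non-hesitant: (0.25 − 0.15)/0.25 = 40% of the hesitant cohort converting.
- If 15% is the share of the cohort still hesitant: 1 − 0.15 = 85% converting. This is the less natural reading, since it discards the 25%.

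**4. What 312 pairs give the planned tests.**

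Paired t-test (noncentral t, 311 df, two-sided 5%):

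| Mean change ÷ SD of change | Power at n = 312 |
|---|---|
| 0.10 | 42% |
| 0.15 | 75% |
| 0.159 | 80% |
| 0.20 | 94% |

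Wilcoxon signed-rank test with normal changes: relative efficiency 0.955, so 0.1591/√0.955 = 0.163 SD. This does not carry over to skewed or heavily tied changes. As a constructed example, take changes of 0 (50%), +0.125 (17%), +0.25 (8%), −0.125 (12%), −0.25 (7%) and −1.0 (6%). The mean is −0.051, the SD 0.267 and the ratio 0.192. In 6,000 simulated samples of 312, with zeros dropped, power was 96% for the t-test and 33% for Wilcoxon. Nothing in the documents supports that distribution. It shows only that one power figure cannot serve both tests.

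**5. In scale points.** The detectable change is 0.1591 × SD: 0.040, 0.080, 0.119 and 0.159 points for assumed SDs of 0.25, 0.5, 0.75 and 1.0. One item moving from agree to strongly agree shifts the mean by (2 − 1)/8 = 0.125. From disagree to agree it shifts by (4 − 2)/8 = 0.25. The t-test has at least 80% power for mean changes of those sizes if the SD is at most 0.125/0.1591 = 0.79 and 0.25/0.1591 = 1.57 respectively.

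**6. Recruitment implied.** 312 hesitant completers at 25% prevalence means 312/0.25 = 1,248 guardians surveyed, before any loss between surveys.

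**The case against.** **312 is ample and this is a pilot.** On the score test 312 pairs detect a small standardised change, the primary analysis can be run as written, and the study is funded and described as a pilot. All of that stands, and it limits the weight of the point. It does not supply the missing justification: the plan makes a formal 80% power claim, and that claim should describe its own analysis.

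**Perhaps everyone is re-surveyed.** One sentence in Interventions and Interactions says that subjects complete a second scale, without repeating the restriction. But it follows directly on the sentence about hesitant subjects, the detailed procedure later in that section covers only those given the intervention, and the sample-size sentence itself equates the 312 completers with hesitant subjects. Re-surveying everyone would in any case leave the test mismatch.

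**Restating power as 0.16 SD is circular.** It is worked back from 312. This is fair, and it is why an assumed SD and a target mean change have to accompany it.

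**A detectable change is not a detectable intervention effect.** The cohort is selected on a high first score and has no control arm, so regression to the mean alone lowers the second score. Assume bivariate normal scores with the top 25% selected and no intervention effect. The expected fall is then 0.42, 0.29 and 0.20 SD of the change at test-retest correlations of 0.8, 0.9 and 0.95. The documents give no reliability figure, so the size is uncertain. This is a separate question of interpretation and does not rescue the power statement, but the restated sentence should not be read as power for an effect of the education.

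**Conclusion.** The concern holds. The Aim 2 power statement describes a comparison that cannot occur in the enrolled cohort and a test that the plan does not include. Both mismatches are visible in the text and depend on no calculation, on no guess about how 312 was obtained, and not on the 15% to 15% slip.

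What is shown is an unsupported rationale, not a shortage of subjects. The detectable change of 0.159 SD rests on a two-sided 5% level, 312 completed pairs and the paired t-test. The figure of about 0.163 SD for Wilcoxon also needs approximately normal changes. The conversion to 0.04 to 0.16 scale points rests on an assumed SD of 0.25 to 1.0. The statement should be corrected, but the error does not prevent the planned analysis.

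**What to change.** Replace the 25%-to-15% power sentence by one of two routes, at the team's choice.

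**(a) Score change.** For example: *Among participants with a baseline mean score of 3 or more, 312 completed pairs give 80% power (two-sided 5%, paired t-test) to detect a mean score change of 0.16 SD of the change.* Add an assumed SD and the mean change considered meaningful. For Wilcoxon, say only that the figure is about 0.163 SD if changes are approximately normal. Note that this is power for a before-after change in a selected, uncontrolled group. The cost is rewording. The weakness is that 0.16 SD justifies nothing until the team supplies the SD and target.

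**(b) Conversion.** Define the proportion of the hesitant cohort scoring below 3 at the second survey, from a 100% baseline. Add it to the Analytical Plan with a confidence interval, or with a null value and test that the team justifies. A null of 0% would not serve, because a single conversion would reject it. Say which reading of 25% to 15% was meant. If the observed result equalled the target, the 95% Wilson interval would be 34.8% to 45.6% for 40% (125/312) or 80.5% to 88.5% for 85% (265/312). The cost is one added endpoint definition. The weakness is that this rate has no natural null.

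Under either route, keep the statement that the 312 are hesitant completers and add the implied 1,248 guardians surveyed at 25% prevalence, before loss between surveys.
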